#### ACKNOWLEDGEMENTS

The RECEDE study is funded by the National Institute of Health Research (NIHR Health Service and Delivery Research). The views expressed are those of the authors and not necessarily those of the NIHR or the Department of Health and Social Care.

IRAS 282247\_RECEDE protocol\_v2.2\_11.02.2022 Page **3** of **50** 

#### **STUDY SUMMARY**

	Objectives Outcome Measures
Planned study period	40 months
Sample size	1915
Study arms	All participants will receive the index tests: stool FIT and urine VOCs; and reference standard: full colonoscopy examination or CTC.
	Stool FIT and urine VOC
Reference standard Index tests	Final report from the CTC or colonoscopy examination and confirmatory histology report Stool FIT alone
Study participants	Participants referred from primary care to NHS Trusts that undertake colonoscopy or CTC will be approached to participate.
Study design	Multicentre – Prospective Diagnostic Accuracy Study
	*Significant Bowel Disease (SBD) is defined as those with colorectal cancer, significant pre-malignant polyps (adenomas with size >10mm or with high grade dysplasia)or inflammatory bowel disease
	If stool FIT plus urine VOC is sufficiently accurate it will enable a reduction in the number of colonoscopies and Computed Tomography Colonography (CTC) in those without SBD.
Study aim	To investigate the diagnostic accuracy of stool FIT plus urine VOC compared to stool FIT alone for detection of SBD*.
Research question	Can the addition of urine VOC to stool FIT testing rule out significant bowel disease (SBD) and by so doing, reduce unnecessary invasive tests (colonoscopy/CTC) – the right test for the right participant?
Study title	Reducing Colonoscopies in patients without significant bowEl DiseasE - RECEDE study

Primary	Diagnostic accuracy of stool FIT plus urine VOC compared to stool FIT alone to improve detection of SBD.	Sensitivity, specificity, negative predictive value (NPV) and positive predictive value (PPV) of stool FIT plus
		urine VOC in detection of SBD, using CTC or colonoscopy histology findings.
Secondary	Diagnostic accuracy of stool FIT plus urine VOC in detection of SBD	Receiver operating characteristic (ROC) curve of stool FIT plus urine VOC in detection of SBD.
	Impact on number of colonoscopies and CTCs undertaken	Calculation of potential number of colonoscopies and CTCs avoided in those without SBD.
	Cost effectiveness and colonoscopy/CTC disutility	Cost calculation, Quality of life (EQ-5D-5L) and quality adjusted life years (QALY) associated with utility of each diagnostic strategy (stool FIT and urine VOC)

Key Words:

FIT, urine VOC, diagnostic, colorectal cancer, adenoma, IBD, colonoscopy

Diagnostic Accuracy Study Subject recruitment: Participants with lower GI symptoms (non-urgent) And urgent referrals as per current NICE guidelines n=1915

Post participant PIS, consent form & invitation letter Telephone to confirm interest in participation

#### Face to face

Approach participant during clinic following CTC or colonoscopy referral. Consent Baseline CRF data EQ-5D-5L Questionnaire Collect Urine samples for VOC analysis. Provide stool sample collection FIT kit. Participant posts stool sample to Rugby Bowel Cancer Screening Hub.

#### Remote

Phone participant when CTC or colonoscopy referral confirmed. Consent (remote) Baseline CRF data EQ-5D-5L Questionnaire Post urine and stool sample collection kits. Participant posts sample to Rugby Bowel Cancer Screening Hub and brings/posts urine sample to hospital.

#### CTC or Colonoscopy appointment

EQ-5D-5L and Resource Use Questionnaire **before** colonoscopy Complete CTC or colonoscopy

EQ-5D-5L Questionnaire 24 hours after colonoscopy or CTC EQ-5D-5L Questionnaire 72 hours post colonoscopy or CTC

EQ-5D-5L and resource use questionnaire 3 weeks post colonoscopy or CTC Adverse outcomes follow up

#### Figure 1 Study flow chart.

#### Note - EQ-5D-5L questionnaire only to be requested at sponsor site (UHCW)

Abbreviations: GI, Gastrointestinal; PIS, Participant Information Sheet; CRF, Case Report Form; FIT, Faecal Immunochemical Test for haemoglobin; VOC, Volatile Organic Compounds.

IRAS 282247\_RECEDE protocol\_v2.2\_11.02.2022 Page 8 of 50

#### SCHEDULE OF EVENTS

**Table 1** Schedule of events for collection of stool FIT and urine VOC for both face-to-face and remote
 recruitment scenarios.

Face to Face:

Observation	Baseline (referral visit)	Day of colonoscopy or CTC (before procedure)	24hrs & 72hrs post colonoscopy or CTC	3 weeks post colonoscopy or CTC	Analysis complete and results available
Eligibility screening					
	Х				
Informed consent	Х				
Baseline data	Х				
Urine sample for VOC analysis	Xª				
Stool sample for FIT test	Xp				
Participant questionnaires: EQ-5D*	Xc	х	Xc	Xc	
Resource use questionnaire*		х		Xc	
Colonoscopy or CTC					
results and adverse				Х	
outcomes					
Follow Up in CTC					Х
negative patients					

Remote:

Observation	Baseline (remotely)	Pre- colonoscopy or CTC (participant at home)	Day of colonoscopy or CTC (before procedure)	24hrs and 72hrs post colonoscopy or CTC	3 weeks post colonoscopy or CTC	Analysis complete and results available
Eligibility screening	х					
Informed consent	X (via telephone)					
Baseline data	Х					
Urine sample for VOC analysis (kit to be posted to participant)		Xď				
Stool sample for FIT test (kit to be posted to participant)		Xp				

Participant	VC	V	M	XC	
questionnaires:	Xc	Х	Xc	Xc	
EQ-5D*					
Resource use		V		VC	
questionnaire*		Х		Xc	
Colonoscopy or					
CTC results and				х	
adverse				^	
outcomes					
Follow Up in CTC					Х
negative patients					

Note - all sample collections are designed to be timed, if possible, with participant's attendance to clinic or treatment to minimise additional visits. If this is not feasible, there is a postal option or delivery to local GP for transport to central site only\*

- (a) If participant is unable to provide a urine sample at Baseline, they can return sample to their GP surgery\* or drop it off at the hospital. If this is not possible, participants also have the option to collect a urine sample, 24 hours prior to bowel prep, and bring it with them on the day of colonoscopy/CTC (participant will have to keep the sample in the freezer and, if required, place in a provided cool bag when bringing back to the hospital if sample is likely to be out the freezer for over 1 hour)
- (b) Only provide participant with FIT testing kit and pre-paid envelope for stool sample collection at home if it will be 4 weeks between their first referral FIT test and their colonoscopy/CTC appointment.
- (c) Both paper, electronic and telephone versions of questionnaires will be made available depending on site and participant preference. If a paper option is preferred, provide the participant with a pre-paid envelope to return questionnaire(s) or collect on the day of colonoscopy or CTC if possible.
- (d) Provide participant with VOC testing kit and optional cool bag (if required) for urine sample collection at home. Also provide pre-labelled envelope if returning their sample via their GP courier service.
- (e) Participants medical records will be checked prior to contacting participant for follow up

\*Note –questionnaires only to be requested at sponsor site (UHCW)

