NHS England has suggested that FIT may be used in secondary care to triage timing of colonoscopy or CTC rather than need for colonoscopy or CTC, or to discharge patients if FIT is returned negative. This is because there is recognition of the lack of evidence to guide referral for colonoscopy or CTC. This is the very reason for undertaking the RECEDE study. NHS England guidance also actively encourages primary care physicians to continue to refer to secondary care all those with lower GI symptoms and not to delay or defer such referrals.

In summary, it is likely there will be a population (unable to estimate proportion at this time) that will have had a FIT test prior to their colonoscopy or CTC. The time interval from FIT test to colon investigation will be highly variable hence for participants into RECEDE, we will still re-test FIT alongside urine VOC as originally planned if the participant has a wait of over 4 weeks between their first FIT test and their colonoscopy or CTC. If their colon investigation is scheduled within 4 weeks of the first FIT test (i.e. for urgent referrals) then we will be able to use the first test alongside VOC analysis for the primary outcome analysis and not need to request a second test. The initial FIT test will be purely to triage *timing* of colonoscopy or CTC rather than *need* for colonoscopy or CTC. Due to limited capacity, initial recruitment rate will be slower, possibly only half the rate of what was previously predicted for the next 12 months but the aims of RECEDE are still achievable.

FIT kits are fairly uniform across practices - both HMJac-K and OC-Sensor are most commonly used, however these kits collect different quantities of faecal matter into different buffer volumes and so cannot be directly compared. However a conversion factor is available in order to equalise the tests (71). Therefore if a recruiting site uses a FIT test other than the HMJac-k to triage their patients we are able to accurately compare the two.

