#### **6 STUDY PROCEDURES**

Recruitment options will be tailored to the respective site either remotely or at time of clinic visit. This is shown in Appendix B Figures 1 and 2. If the clinician decides that colonoscopy or CTC is required the participant will then be invited to participate in the RECEDE study – see Figure 1.

Informed consent will be obtained and Case Report Forms (CRFs) completed and questionnaires (EQ-5D) handed out at the same time (questionnaires will only be requested at the sponsor site - UHCW). The participant will be requested to provide a stool sample from home and post for analysis, which must be at least 24 hours before starting bowel cleansing medication. Urine samples can be collected either during a clinic visit (preferential) or, if this is not possible, at home and either sent via GP courier back to the hospital or hand delivered by the participant on a future visit to the hospital that aligns with standard care at the recruiting site. Participants are requested to record date and time when samples are collected. Participants may be provided with cool bags if collecting urine from home, if participant needs to freeze their sample at home and the sample is likely to be out of the freezer for longer than 1 hour before returned to the hospital.

For stool samples, a pre-prepared stool collection kit is provided together with return envelope to be posted directly to the Rugby Bowel Cancer Screening Hub – see Figure 4A below. The kit can either be posted to participants or given directly at time of clinic visit (site dependant). Stool samples are required at least 24hrs **prior** to commencing bowel preparation for colonoscopy.

For urine samples (sample collection kit shown in Figure 4B), this can be collected either at the time of a hospital visit or at home (at least 24hrs prior bowel preparation) and kept in a freezer until returned if the sample cannot be returned the same day as it is produced. At site level, the PI may adapt based on local policy. If the sample is frozen at home by the participant, cool bags with ice blocks can be provided to maintain cold chain until deposit at the site freezer. Depending on the site, participants may have the option of returning samples to their respective GPs for transfer to the site. We will aim for the time between the sample being produced and the sample being frozen at -80°c to be <4 hours, unless the participant freezes their sample at their home first.

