#### 8.2.2 Primary outcome analysis

The primary outcome is diagnostic accuracy - sensitivity, specificity, NPV and PPV of the dual index test, FIT and VOC. A FIT result that is >10 µgHb/g faeces OR a VOC result with predicted probability >0.63 implies that the participant is defined as having SBD and need to be referred for colonoscopy. We will report 2x2 tables of test accuracy of the dual test by the reference standard (final report from the CTC or colonoscopy examination and confirmatory histology report of SBD which is either colon cancer, colorectal adenomas or inflammatory bowel disease), alongside summary measures of sensitivity, specificity, NPV and PPV, and their 95% confidence intervals. Confidence intervals for sensitivity and specificity estimates that are very close to 1.0 will be according to the Zhou-Li method and the intervals for NPV and PPV estimates that are very close to 1.0 will be according to the Bayesian method (38). These test accuracy estimates will be used in the economic model.

We will analyse the combined FIT+VOC test results as both parallel (results from both tests are interpreted in combination) and serial testing (VOC performed only if FIT negative, i.e. <10  $\mu$ gHb/g faeces). The "or" rule will be considered in the interpretation of both parallel and serial tests where the diagnosis is positive when either test is positive (FIT >10  $\mu$ gHb/g faeces and/or VOC predicted probability >0.63), and negative when both are negative (FIT <10  $\mu$ gHb/g faeces and VOC predicted probability <0.63). In the serial test, if the FIT is positive (FIT >10  $\mu$ gHb/g faeces) then the diagnosis is positive. Otherwise, use the result from VOC and if it is positive (VOC predicted probability >0.63) then the diagnosis is positive. If the VOC result is also negative then the diagnosis is negative. Mathematically, both methods would give the same diagnostic results but would make a difference in the economic model.

A 2x2 table of test accuracy for each individual index test by the reference test will also be presented. Sensitivity, specificity, PPV and NPV will also be presented with their 95% confidence intervals for FIT only and VOC only. Participants with missing data for either of the index tests (FIT or VOC) or the reference standard (colonoscopy) will be excluded from this analysis.

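### Schedule note (b), read literally, withholds the FIT kit from participants with no earlier FIT, contradicting the flow chart, section 6 and the re-test purpose in section 1.6

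*Protocol*

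**What the plan says.** **Schedule of Events, Table 1, note (b).** "Only provide participant with FIT testing kit and pre-paid envelope for stool sample collection at home if it will be 4 weeks"; the sentence goes on to define the interval as running from the first referral FIT to the procedure appointment. The note is attached to the stool-sample row in both the face-to-face and the remote schedule.

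**Places that set no such condition.**
- The Study Summary, under study arms, gives both index tests to all participants.
- Figure 1, face-to-face box: "Provide stool sample collection FIT kit".
- Figure 1, remote box: "Post urine and stool sample collection kits".
- Section 6, request: "The participant will be requested to provide a stool sample from home and post for analysis".
- Section 6, supply: "a pre-prepared stool collection kit is provided together with return envelope to be posted directly to the Rugby Bowel Cancer Screening Hub".

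**Section 1.6.** The authors write that "it is likely there will be a population (unable to estimate proportion at this time) that will have had a FIT test prior" to the procedure. A participant whose wait since that first FIT exceeds 4 weeks is tested again. If the procedure falls within 4 weeks, the first result is used for the primary outcome and no second sample is requested.

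**Section 5.1.** Entry requires the ability to return both samples. An earlier FIT is not required.

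**Section 8.2.2.** "Participants with missing data for either of the index tests (FIT or VOC) or the reference standard (colonoscopy) will be excluded".

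**The concern.** An instruction of the form only-if sets a necessary condition. A participant who has never had a FIT cannot meet a condition measured from a first FIT, and note (b) has no branch for that case. Such participants are admitted by section 5.1 and foreseen by section 1.6, which expects only part of the population, of unknown size, to have been tested beforehand. Section 1.6 also describes patients arriving through A&E whose history is not on the hospital system, so an earlier FIT may be unknown at recruitment.

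Section 7.11 sends the reader to Table 1 for the study assessments, so site staff may well work from the table. A site that did so literally would collect no FIT from untested participants. Section 6 requires stool at least 24 hours before bowel preparation starts, so the sample cannot be collected afterwards.

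Two things are at stake. The number of complete cases, and with it the number of SBD cases behind the sensitivity estimate, could fall. And because the loss would depend on whether someone had been tested before, the analysed set could tilt towards participants already FIT-tested, away from the broad referred population the study aims at.

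**Working it through.** **1. Setting the kit rules side by side**

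| Participant | Note (b), literal | Figure 1 and section 6 | Section 1.6 |
|---|---|---|---|
| No earlier FIT | Condition cannot be met: no kit | Kit supplied | Not singled out; FIT testing as originally planned |
| Earlier FIT, wait over 4 weeks | Kit, taking the note to mean 4 weeks or more | Kit supplied | Re-test |
| Earlier FIT, wait exactly 4 weeks | Kit | Kit supplied | No re-test, since not over 4 weeks |
| Earlier FIT, wait under 4 weeks | No kit | Kit supplied | Use first result |

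The first row is the substantive conflict. The third is a boundary mismatch; that participant has a FIT result under either rule, so nothing is lost. In the fourth, Figure 1 and section 6 are themselves broader than section 1.6. All of these places therefore need to be reconciled, not note (b) alone.

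**2. Reproducing the planned size (section 8.1)**

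Inputs: 200 SBD cases, SBD prevalence 0.19, return of both usable samples 0.55, target sensitivity 0.97, 95% CI width 0.05.

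- Participants with both samples: 200 / 0.19 = 1,052.6, so 1,053.
- Total: 1,053 / 0.55 = 1,914.5, so 1,915. This matches the protocol.
- The Zhou-Li equations are not legible in the text, so I used the Wilson interval as a stand-in. Its width is [2z / (1 + z²/n)] × √[p(1 − p)/n + z²/(4n²)]. With n = 200, p = 0.97 and z = 1.96, this is (3.92 / 1.0192) × √(0.0001455 + 0.0000240) = 0.050, in line with the stated 0.05.

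The 55% is a return rate. The calculation contains no term for kits that were never supplied.

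**3. Illustration under the literal reading**

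Let q be the share of participants with no earlier FIT. The protocol gives no value, so q is assumed. I also assume that every site applies note (b) literally, that q is independent of sample return and of SBD, and that the 55% stays fixed.

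Complete cases = 1,915 × 0.55 × (1 − q); SBD cases = complete cases × 0.19.

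| q (assumed) | Complete cases | SBD cases | Wilson width at 0.97 |
|---|---|---|---|
| 0 | 1,053 | 200 | 0.050 |
| 10% | 948 | 180 | 0.053 |
| 25% | 790 | 150 | 0.059 |
| 50% | 527 | 100 | 0.074 |

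Each 10 percentage points of q would remove about 105 complete cases and 20 SBD cases. These are scenarios, not forecasts.

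**The case against.** A reader might infer from note (b) that the protocol denies untested participants a kit, so that they certainly have no FIT and drop out of the primary analysis. The document as a whole does not say that. The Study Summary, both flow-chart boxes and section 6 give the test or kit without condition, and the remote row of the same table says that the kit is to be posted. Section 1.6 explains the 4-week rule: it decides whether someone who already has a FIT needs another. Read with that section, note (b) looks like a compressed instruction not to duplicate a recent test. The reminders for missing samples in section 7.6 also make unnoticed, study-wide non-supply less likely. This stands, and it is why the point is a contradiction with a conditional loss.

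The other objections, and what remains of them:

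- **The size is assumed.** This stands. Section 1.6 says that the proportion with an earlier FIT cannot be estimated, and its account of referral without FIT in most regions describes practice before COVID-19. It cannot be used to argue that most current participants lack a FIT.
- **The fixed 55% may be wrong for those retained.** This stands. The rate is for returning both samples, whereas a participant with a recent FIT on record needs to return only urine. The illustration may therefore overstate the loss.
- **The exclusion sentence has uncertain scope.** This stands in part. It refers to this analysis and sits in the paragraph on the single tests. It closes the primary-outcome section, however, and most naturally covers that analysis. Section 8.2.3 adds missing-data sensitivity analyses, but they cannot supply results for samples never requested.
- **Appendix B may settle the matter.** Only the captions of its recruitment charts are legible in the text used here, so this cannot be checked. Even if the charts are clear, the wording of note (b) would still conflict with them.

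**Conclusion.** The point holds as an internal contradiction. Note (b) states a necessary condition that participants without an earlier FIT cannot meet, while other current text gives the kit or the test to all. A site following the note literally would get a result that the design does not intend: no FIT from eligible participants, who would then be excluded under section 8.2.2 on its most natural reading.

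The loss is conditional on site behaviour, and its size cannot be derived. With assumed shares of 10% to 50% without an earlier FIT, universal literal application and an unchanged 55% return rate, the SBD cases would fall from 200 to between about 180 and 100. The interval width at a sensitivity of 0.97 would grow from 0.050 to between 0.053 and 0.074. A tilt towards participants already FIT-tested is possible under the same condition, but cannot be quantified. The sample-size calculation itself is reproduced and is not in question.

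**What to change.** Reword note (b) in both schedules so that a FIT kit goes to every participant unless a FIT result usable for the study under section 1.6 is already on record. This also covers participants whose earlier result cannot be retrieved.

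Then reconcile Figure 1 (both boxes), note (b), section 1.6 and section 6 on one interval wording, so that a wait of exactly 4 weeks falls on one side only. Check the Appendix B charts against the same wording.

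The cost is one sentence in the schedule, matching edits in the other places and a short memo to sites. The design, analysis and sample size do not change. The protocol gives no kit budget, so I make no claim about kit costs; the change asks for no more kits than Figure 1 and section 6 already provide for.

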#### LIST OF ABBREVIATIONS

-			
BCSP	Bowel Cancer Screening Programme		
CI	Confidence interval		
CRC	Colorectal cancer		
CRF	Case Report Form		
СТС	Computed Tomography Colonography		
DAS	Diagnostic accuracy study		
FCP	Faecal Calprotectin		
FIT	Faecal Immunochemical Testing		
GCP	Good Clinical Practice		
IBD	Inflammatory Bowel Disease		
IBS	Irritable Bowel Syndrome		
ISF	Investigator Site File		
NHS R&D	National Health Service Research & Development		
PI	Principal Investigator		
PIC	Participant Identification Centre		
PIS	Participant Information Sheet		
REC	Research Ethics Committee		
SDV	Source Data Verification		
SBD	Significant bowel disease		
SOP	Standard Operating Procedure		
SSI	Site Specific Information		
SMF	Study Master File		
TMG	Study Management Group		
TSC	Trial Steering Committee		
VOC	Volatile organic compounds		

